#### b. Previous exposure of human beings with the test product(s) and/or products with a similar biological mechanism

see a

#### c. Can the primary or secondary mechanism be induced in animals and/or in ex-vivo human cell material?

no

#### d. Selectivity of the mechanism to target tissue in animals and/or human beings

n/a

#### e. Analysis of potential effect

n/a

#### f. Pharmacokinetic considerations

we refer to chapter 5.2

#### g. Study population

we refer to chapter 4

#### h. Interaction with other products

n/a

i. Predictability of effect

see e.

j. Can effects be managed?

n/a

**13.2 Synthesis**

Based on previous observational studies, the risks of this RCT are acceptable. We expect a comparable to slightly higher risk of intracranial hemorrhage in the immediate CAS group, but an increased chance of favorable outcome in the immediate CAS group. If the effect of immediate CAS is not worse than the deferred treatment strategy, it will be of great benefit to the patients, by avoiding a second surgical treatment and it will also reduce health care costs. The burden of the study is low.

## 15. TABLES

### 15.1 Modified Rankin Scale (mRS)

Modified Rankin Scale	
0	No symptoms
1	No significant disability. Able to carry out all usual activities, despite some symptoms.
2	Slight disability. Able to look after own affairs without assistance, but unable to carry out all previous activities.
3	Moderate disability. Requires some help, but able to walk unassisted.
4	Moderate severe disability. Unable to attend to own bodily needs without assistance, and unable to walk unassisted.
5	Severe disability. Requires constant nursing care and attention, bedridden, incontinent.
6	Dead

## 15.2 National Institute of Health Stroke Scale (NIHSS)

1a—Level of consciousness	0 = Alert; keenly responsive 1 = Not alert, but arousable by minor stimulation 2 = Not alert; requires repeated stimulation 3 = Unresponsive or responds only with reflex
1b—Level of consciousness questions: What is your age? What is the month?	0 = Answers two questions correctly 1 = Answers one question correctly 2 = Answers neither questions correctly
1c—Level of consciousness commands: Open and close your eyes Grip and release your hand	0 = Performs both tasks correctly 1 = Performs one task correctly 2 = Performs neither task correctly
2—Best gaze	0 = Normal 1 = Partial gaze palsy 2 = Forced deviation
3—Visual	0 = No visual lost 1 = Partial hemianopia 2 = Complete hemianopia 3 = Bilateral hemianopia
4—Facial palsy	0 = Normal symmetric movements 1 = Minor paralysis 2 = Partial paralysis 3 = Complete paralysis of one or both sides
5—Motor arm Left arm Right arm	0 = No drift 1 = Drift 2 = Some effort against gravity 3 = No effort against gravity 4 = No movement
6—Motor leg Left leg Right leg	0 = No drift 1 = Drift 2 = Some effort against gravity 3 = No effort against gravity 4 = No movement
7—Limb ataxia	0 = Absent 1 = Present in one limb 2 = Present in two limbs
8—Sensory	0 = Normal; no sensory loss 1 = Mild-to-moderate sensory loss 2 = Severe-to-total sensory loss
9—Best language	0 = No aphasia; normal 1 = Mild-to-moderate aphasia 2 = Severe aphasia 3 = Mute; global aphasia
10—Dysarthria	0 = Normal 1 = Mild-to-moderate dysarthria 2 = Severe dysarthria
11—Extinction and inattention	0 = No abnormality 1 = Visual, tactile, auditory, spatial, or personal inattention 2 = Profound hemi-inattention or extinction
Score = 0–42	

### 15.3 Extended thrombolysis in cerebral infarction (e-TICI) score

[figure not shown]
Score	Extended Thrombolysis in Cerebral Infarction Scale
0	No reperfusion or anterograde flow beyond site of occlusion
1	Penetration but no perfusion. Contrast penetration exists past the initial obstruction but with minimal filling of the normal territory
2	Incomplete perfusion wherein the contrast passes the occlusion and opacifies the distal arterial bed but rate of entry of clearance from the bed is slower or incomplete when compared to non-involved territories
2a	Some perfusion with distal branches filling of < 50% of territory visualized
2b	Substantial perfusion with distal branches filling of ≥ 50% of territory visualized
2c	Near complete perfusion except for slow flow in a few distal cortical vessels, or presence of small distal cortical emboli
3	Complete perfusion with normal filling of all distal branches

### 15.4 Collateral score baseline CT angiography

Category	Score	Description
None	0	Absent collaterals
Poor	1	Collaterals filling ≤50% of the occluded territory
Intermediate	2	Collaterals filing >50%, but <100% of the occluded territory
Good	3	Collaterals filling 100% of the occluded territory

### 15.5 ASPECT score

Alberta Stroke Program Early CT Score (ASPECTS) is a 10-point systematic quantitative topographic CT scan scoring system, to assess early ischemic changes on pretreatment NCCT in patients with acute ischemic stroke in the territory of the middle cerebral artery. Segmental assessment of the MCA vascular territory is made, and for every defined region of ischemic change, such as focal swelling or parenchymal hypoattenuation, one point is subtracted from the initial score of 10. A score of 10 indicates a normal scan and a score of 0 diffuse ischemia throughout the territory of the MCA.

### 15.6 Arterial occlusive lesion (AoL) Score

[figure not shown]
Score	Description
0	No recanalization of the primary occlusive lesion
1	Incomplete or partial recanalization of the primary occlusive lesion with no distal flow
2	Incomplete or partial recanalization of the primary occlusive lesion with any distal flow
3	No recanalization of the primary occlusive lesion

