#### 8.1.2 Secondary study parameters/endpoints (if applicable)

Secondary endpoints are:

- mRS score of 0-1 at 90 days
- mRS score of 0-2 at 90 days
- mRS score of 0-3 at 90 days
- NIHSS score at 24 hours and day 5-7, or at discharge
- adequate recanalization after EVT (TICI 2b or higher)
- final infarct volume on brain CT at 24 hours
- arterial occlusive lesion (AOL) score on CTA at 24 hours
- any stroke within 90 days
- recurrent ipsilateral TIA/ischemic stroke within 90 days
- Carotid artery re-occlusion at 24 hours and 90 days.
- Mortality at 90 days
- Quality of life (EQ5D-5L) questionnaire at 90 days

For the purpose of health economic evaluation, additional questionnaires will be sent to the study participants at 90 days for measuring loss of productivity (IMTA productivity cost questionnaire (iPCQ)) and medical consumption (IMTA medical consumption questionnaire (iMCQ)).

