### **10.3 Secondary study parameter(s)**

Secondary effect parameters will be assessed with linear, logistic or ordinal regression, where appropriate, with the same adjustments as reported in 10.1.

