## **18.3 Imaging at 24 hours**

### **WHEN**

1. 24 hours after undergoing endovascular treatment a NCCT and CTA (24 hours +/- 12h) should be performed to assess treatment efficacy.
2. If clinically required (i.e. in cases of clinical deterioration of the patient) additional imaging as needed, at the discretion of the treating physician is acquired.

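### Table 15.6 defines AOL score 3 with the same sentence as score 0, so this secondary endpoint has no code for complete recanalization

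*Protocol*

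**What the plan says.** Protocol section 8.1.2 names "arterial occlusive lesion (AOL) score on CTA at 24 hours" among the secondary endpoints. Section 15.6 gives the scale as four rows:

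- score 0: "No recanalization of the primary occlusive lesion"
- score 1: "Incomplete or partial recanalization of the primary occlusive lesion with no distal flow"
- score 2: "Incomplete or partial recanalization of the primary occlusive lesion with any distal flow"
- score 3: word for word the same sentence as score 0

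Section 10.3 sets the analysis: "Secondary effect parameters will be assessed with linear, logistic or ordinal regression, where appropriate". Section 18.3 states the purpose of the 24-hour non-contrast CT and CTA, which "should be performed to assess treatment efficacy", and has all series sent to the core lab. No other section of the protocol defines the AOL score.

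**The concern.** A score that is analysed by regression needs categories that are distinct and that run in one direction. As printed, the AOL scale meets neither condition. Its lowest and highest codes share one definition, and the state a successful procedure aims for has no definition at all.

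The table is the written definition of an efficacy endpoint, so it cannot be set aside as background. A reading form or eCRF label copied from it would carry the fault into the data. Patients whose vessel stayed closed could then be entered with the highest score. Patients with full recanalization could be left unscored or placed one category too low. Section 8.2 states that secondary endpoints are not assessed blind, which makes an unambiguous written definition more useful here.

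**Working it through.** No arithmetic applies, because the protocol states no figure that depends on this table. The check compares the four definitions with one another, with the neighbouring scales and with the planned analysis.

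**Step 1. The codes against the states they should describe.**

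| True state of the target vessel at 24 hours | Code(s) that fit table 15.6 as printed |
|---|---|
| No recanalization | 0 and 3 |
| Partial, no distal flow | 1 |
| Partial, some distal flow | 2 |
| Complete | none |

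Four codes carry three distinct meanings. Read from 0 to 3, the sequence is none, partial, better partial, none. It is not monotone.

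**Step 2. What the protocol itself implies row 3 should be.** Rows 1 and 2 are labelled incomplete or partial and they ascend, which implies a complete category above them. The two neighbouring scales also rise to a best state at score 3. In section 15.3 the top e-TICI score is "Complete perfusion with normal filling of all distal branches". In section 15.4 collateral score 3 is full filling of the occluded territory. Only the AOL table returns to its starting category. The evidence within the document therefore points to row 0 having been copied into row 3.

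**Step 3. What the analysis would do with each way of reading the table.**

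- A reader ignores the text of row 3, codes complete as 3 and none as 0. The recorded order is correct and the regression is unaffected.
- A reader codes some patients without recanalization as 3. Failures then sit above both partial categories, and code 3 may mix failures with full successes. Linear and ordinal models lose their ordering. A logistic model on a cut-point places those patients on the wrong side.
- A reader follows the text and finds no code for complete recanalization. The score is left blank or entered as 2, so the best outcomes are missing or understated.

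**Step 4. What depends on the table.** Section 8.1.2 lists twelve secondary endpoints, and AOL is one of them. Recanalization after EVT (TICI 2b or higher) is a separate endpoint with its own scale in section 15.3. The primary endpoint is the mRS at 90 days. Neither the non-inferiority decision in section 10 nor the sample size in section 4.5 uses AOL.

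**The case against.** The strongest reply is that no harm need follow. Section 18.3 sends the 24-hour CTA to an imaging core lab, and section 19 provides for an independent imaging assessment committee. Specialist readers are likely to know the scale, and rows 1 and 2 make the intended meaning of row 3 plain. The reading form and the eCRF are not part of the protocol, and nothing shows that they repeat the slip. This stands: the harm is possible, not demonstrated.

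A second reply is that text taken from a PDF can be damaged, and a figure beside the table is not shown. A duplicated row cannot be wholly excluded without the source page. It is an unlikely explanation, because the row is a complete sentence and the other three rows are intact.

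A third reply is that endpoint coding belongs in the statistical analysis plan. That would answer a complaint that something is missing. Here the protocol gives a definition and the definition is wrong, and it would remain wrong even if another document were correct.

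Two stronger readings are tempting, and the documents support neither.

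- A reader might infer that every fully recanalized patient would be misclassified, which could be a large share of the trial. The protocol gives no rate of complete recanalization at 24 hours. Such patients, if coded 3, would also be correctly ordered despite the wrong label. The damaging error is coding patients without recanalization as 3, and its frequency is unknown.
- A reader might infer that the treatment effect on this endpoint could be reversed. That would need systematic coding of no recanalization as 3, although code 0 already says exactly that and the scans go to a core lab. Nothing in the protocol suggests it.

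**Conclusion.** The definition is wrong as written. Scores 0 and 3 are identical, complete recanalization has no code, and nothing else in the protocol corrects the table. This rests on the wording alone and needs no assumption about recanalization rates.

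The consequence is limited. One of twelve secondary endpoints could be distorted, and only if the printed table is what the readers or the data-entry form follow. The size of any distortion cannot be stated from the protocol. The primary mRS analysis, the non-inferiority conclusion, the sample size and the TICI endpoint are unaffected. It is a small error that is worth correcting because the table is the endpoint's only written definition.

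**What to change.** Change row 3 of table 15.6 to complete recanalization of the primary occlusive lesion. Then confirm that the core-lab reading form and the eCRF carry the same four definitions as the corrected table. If both already do, nothing more is needed. If either reproduces the printed error, re-check the AOL reads made with that form. The cost is one table cell in the next amendment and a short comparison of two forms.

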## 16. FIGURES

### 16.1 Figure 1: CASES trial logo

[figure not shown]

### 16.2 Figure 2: Patient flow in the trial

\* not part of standard care

16.3 Figure 3: Flowchart of deferred consent procedure for the CASES trial

Based on the flowchart proxy-deferred consent in emergency critical care research.

## 17. QUESTIONNAIRES

### 17.1 EuroQoL 5D-5L Dutch (versie 1.1, Paper Self-Complete)

Zet bij iedere groep in de lijst hieronder een kruisje in het hokje dat het best past bij uw gezondheid VANDAAG.

#### MOBILITEIT

- Ik heb geen problemen met lopen
- Ik heb een beetje problemen met lopen
- Ik heb matige problemen met lopen
- Ik heb ernstige problemen met lopen
- Ik ben niet in staat om te lopen

#### ZELFZORG

- Ik heb geen problemen met mijzelf wassen of aankleden
- Ik heb een beetje problemen met mijzelf wassen of aankleden
- Ik heb matige problemen met mijzelf wassen of aankleden
- Ik heb ernstige problemen met mijzelf wassen of aankleden
- Ik ben niet in staat mijzelf te wassen of aan te kleden

#### DAGELIJKSE ACTIVITEITEN *(bijv. werk, studie, huishouden, gezins- en vrijetijdsactiviteiten)*

- Ik heb geen problemen met mijn dagelijkse activiteiten
- Ik heb een beetje problemen met mijn dagelijkse activiteiten
- Ik heb matige problemen met mijn dagelijkse activiteiten
- Ik heb ernstige problemen met mijn dagelijkse activiteiten
- Ik ben niet in staat mijn dagelijkse activiteiten uit te voeren

#### PIJN / ONGEMAK

- Ik heb geen pijn of ongemak
- Ik heb een beetje pijn of ongemak
- Ik heb matige pijn of ongemak
- Ik heb ernstige pijn of ongemak
- Ik heb extreme pijn of ongemak

[figure not shown]
#### ANGST / SOMBERHEID

- Ik ben niet angstig of somber
- Ik ben een beetje angstig of somber
- Ik ben matig angstig of somber
- Ik ben erg angstig of somber
- Ik ben extreem angstig of somber

- We willen weten hoe goed of slecht uw gezondheid VANDAAG is.
- Deze meetschaal loopt van 0 tot 100.
- 100 staat voor de beste gezondheid die u zich kunt voorstellen.  
0 staat voor de slechtste gezondheid die u zich kunt voorstellen.
- Markeer een X op de meetschaal om aan te geven hoe uw gezondheid VANDAAG is.
- Noteer het getal waarbij u de X heeft geplaatst in onderstaand vakje.

UW GEZONDHEID VANDAAG =

De beste  
gezondheid die u  
zich kunt  
voorstellen

De slechtste  
gezondheid die u  
zich kunt  
voorstellen

## 17.2 EuroQoL 5D-5L English (version 1.2, Paper Self-Complete)

Under each heading, please tick the ONE box that best describes your health TODAY.

### MOBILITY

- I have no problems in walking about
- I have slight problems in walking about
- I have moderate problems in walking about
- I have severe problems in walking about
- I am unable to walk about

### SELF-CARE

- I have no problems washing or dressing myself
- I have slight problems washing or dressing myself
- I have moderate problems washing or dressing myself
- I have severe problems washing or dressing myself
- I am unable to wash or dress myself

### USUAL ACTIVITIES *(e.g. work, study, housework, family or leisure activities)*

- I have no problems doing my usual activities
- I have slight problems doing my usual activities
- I have moderate problems doing my usual activities
- I have severe problems doing my usual activities
- I am unable to do my usual activities

### PAIN / DISCOMFORT

- I have no pain or discomfort
- I have slight pain or discomfort
- I have moderate pain or discomfort
- I have severe pain or discomfort
- I have extreme pain or discomfort

[figure not shown]
### ANXIETY / DEPRESSION

- I am not anxious or depressed
- I am slightly anxious or depressed
- I am moderately anxious or depressed
- I am severely anxious or depressed
- I am extremely anxious or depressed

- We would like to know how good or bad your health is TODAY.
- This scale is numbered from 0 to 100.
- 100 means the best health you can imagine.  
0 means the worst health you can imagine.
- Please mark an X on the scale to indicate how your health is TODAY.
- Now, write the number you marked on the scale in the box below.

YOUR HEALTH TODAY =

The best health you can imagine

The worst health you can imagine

### 17.3 EuroQoL 5D-5L: French (Version 1.1, Paper Self-Complete)

Pour chaque rubrique, veuillez cocher UNE case, celle qui décrit le mieux votre santé AUJOURD'HUI.

#### **Mobilité**

- Je n'ai aucun problème pour me déplacer à pied
- J'ai des problèmes légers pour me déplacer à pied
- J'ai des problèmes modérés pour me déplacer à pied
- J'ai des problèmes sévères pour me déplacer à pied
- Je suis incapable de me déplacer à pied

#### **Autonomie de la personne**

- Je n'ai aucun problème pour me laver ou m'habiller tout(e) seul(e)
- J'ai des problèmes légers pour me laver ou m'habiller tout(e) seul(e)
- J'ai des problèmes modérés pour me laver ou m'habiller tout(e) seul(e)
- J'ai des problèmes sévères pour me laver ou m'habiller tout(e) seul(e)
- Je suis incapable de me laver ou de m'habiller tout(e) seul(e)

#### **Activités courantes** (EXEMPLES: TRAVAIL, ÉTUDES, TRAVAUX MÉNAGERS, ACTIVITÉS FAMILIALES OU LOISIRS)

- Je n'ai aucun problème pour accomplir mes activités courantes
- J'ai des problèmes légers pour accomplir mes activités courantes
- J'ai des problèmes modérés pour accomplir mes activités courantes
- J'ai des problèmes sévères pour accomplir mes activités courantes
- Je suis incapable d'accomplir mes activités courantes

#### **Douleurs / gêne**

- Je n'ai ni douleur ni gêne
- J'ai des douleurs ou une gêne légère(s)
- J'ai des douleurs ou une gêne modérée(s)
- J'ai des douleurs ou une gêne sévère(s)
- J'ai des douleurs ou une gêne extrême(s)

[figure not shown]
#### **Anxiété / Dépression**

- Je ne suis ni anxieux(se), ni déprimé(e)
- Je suis légèrement anxieux(se) ou déprimé(e)
- Je suis modérément anxieux(se) ou déprimé(e)
- Je suis sévèrement anxieux(se) ou déprimé(e)
- Je suis extrêmement anxieux(se) ou déprimé(e)

- Nous aimerions savoir dans quelle mesure votre santé est bonne ou mauvaise AUJOURD'HUI.
- Cette échelle est numérotée de 0 à 100.
- 100 correspond à la meilleure santé que vous puissiez imaginer. 0 correspond à la pire santé que vous puissiez imaginer.
- Veuillez faire une croix (X) sur l'échelle afin d'indiquer votre état de santé AUJOURD'HUI.
- Maintenant, veuillez noter dans la case ci-dessous le chiffre que vous avez coché sur l'échelle.

VOTRE SANTÉ AUJOURD'HUI =

La meilleure santé  
que vous puissiez  
imaginer

La pire santé que  
vous puissiez  
imaginer

## Vragenlijst over uw gezondheid en werk

Onderzoekers noemen deze vragenlijst de iMTA PCQ. (iPCQ)

### **Toelichting**

#### **Lees dit alstublieft eerst!**

#### **Kunt u de lijst niet zelf invullen?**

Als u de lijst niet zelf kunt invullen, kan iemand u misschien helpen. Bijvoorbeeld een familielid.

#### **Waar gaat de vragenlijst over?**

De vragenlijst gaat over uw gezondheid en werk in de afgelopen 4 weken.

#### **Hoe lang duurt het om de lijst in te vullen?**

Het duurt ongeveer 10 minuten om de lijst in te vullen.

#### **Hoe moet u de lijst invullen?**

- Begin bij de eerste vraag en volg de nummering.
- Bij sommige vragen kunt u tekst of een getal invullen, bij andere vragen kunt u een hokje/optie aanklikken/aankruisen
- U kunt geen foute antwoorden geven.

#### **Wat gebeurt er met uw antwoorden?**

Uw antwoorden worden gebruikt voor onderzoek. Alleen de onderzoekers zien uw antwoorden. Dus niemand anders.

De onderzoekers schrijven uw naam nergens op. En zij vertellen aan niemand dat u aan het onderzoek heeft meegewerkt.

#### **Fijn dat u de lijst voor ons wilt invullen!**

**Vraag 1. Wat doet u in het dagelijks leven?** Kruis aan wat u de meeste tijd doet.

- Ik zit op school, ik studeer
- Ik werk in loondienst
- Ik ben zelfstandig ondernemer
- Ik ben huisvrouw, huisman
- Ik ben werkloos
- Ik ben arbeidsongeschikt, voor ... %
- Ik ben met pensioen of prepensioen
- Ik doe iets anders, namelijk .....

**Vraag 2. Hebt u betaald werk?**

- Nee
- Ja

De volgende vragen gaan over uw baan. Dus over werk waarvoor u betaald wordt. Hebt u geen betaalde baan? Ga dan verder met vraag 12. Lees eerst de toelichting boven vraag 12.

**Vraag 3. Wat is uw beroep?**

.....

**Vraag 4. Hoeveel uur per week werkt u?** Tel alleen de uren waarvoor u betaald wordt.

..... uren

**Vraag 5. Op hoeveel dagen in de week werkt u?**

Op..... dagen

**Vraag 6. Bent u in de afgelopen 4 weken afwezig geweest van uw werk omdat u ziek was?**

- Nee
- Ja, ik ben ..... dagen afwezig geweest

(Tel alleen de werkdagen in de afgelopen 4 weken)

Heeft u "Ja" geantwoord? Beantwoord dan vraag 7.

Ga anders verder met vraag 9.

**Toelichting bij vraag 12**

Ook bij onbetaald werk, kunt u last hebben van uw lichamelijke of psychische problemen. Soms kunt u daardoor minder doen. U kunt bijvoorbeeld niet goed voor de kinderen zorgen of vrijwilligerswerk doen. Of geen boodschappen doen of in de tuin werken. Daarover gaan de volgende vragen.

**Vraag 12. Waren er dagen waarop u minder onbetaald werk kon doen door uw lichamelijke of psychische problemen?** Het gaat om dagen in de afgelopen 4 weken.

- Nee
- Ja

Heeft u “Ja” geantwoord? Beantwoord dan vraag 13 en 14.  
Anders was dit de laatste vraag.

**Vraag 13. Op hoeveel dagen was dit zo?** Tel alleen de dagen in de afgelopen 4 weken. ....  
dagen

**Vraag 14. Stel dat iemand, bijvoorbeeld uw partner, familielid of een bekende, u op deze dagen had geholpen. En al het onbetaalde werk wat u niet kon doen, voor u had gedaan. Hoeveel uur was die persoon hier op deze dagen dan gemiddeld mee bezig geweest?**

Gemiddeld..... uur op deze dagen

**Dit was de laatste vraag.**

**Heeft u vragen of opmerkingen?**

Misschien heeft u nog vragen of opmerkingen? Schrijft u deze dan hieronder op.

.....  
.....

**Hartelijk dank!**

## 17.5 Institute for Medical Technology Assessment Productivity Costs Questionnaire (iMTA PCQ) - English (Version 2.0, 14/07/2023)

UK version

